Title: Testing a Neurocognitive Model of Distancing Using Transcranial Magnetic Stimulation

Duke University IRB Protocol: Pro00100171

ClinicalTrials.gov Identifier: NCT03698591

Study Protocol and Statistical Analysis Plan

Reference date: September 18th, 2018

Research Summary

1. **Protocol Title:** Testing a neurocognitive model of distancing using transcranial magnetic stimulation
2. **Purpose of study:** Distancing is a type of cognitive emotion regulation that relies on self-projection, or the ability to shift perspective from the here and now to a simulated time, place, or person.¹ Based on our own review and meta-analysis of the distancing literature, we have developed a model of the neurocognitive processes of distancing,² which are currently not well understood.³ The goal of this project is to test specific neurocognitive relationships from this model using transcranial magnetic stimulation (TMS). This testing will serve the broader purpose of improving scientific knowledge regarding the neural bases of 1) cognitive emotion regulation and 2) simulating and shifting perspectives in healthy adults. Additionally, it will assess the feasibility of modulating emotion regulation performance via constituent processes of distancing using TMS in healthy adults.

Primary Objective: Test the causal influence of cortical brain areas on the cognitive processes of distancing as defined in our model.

Measurement: We will apply TMS to cortical targets to modulate local neural activity during performance of a distancing task. The effect of stimulation will be evaluated by contrasting distancing performance with active stimulation against distancing performance with sham stimulation for each participant. Distancing performance will be assessed through self-reported valence, matching our previous studies of distancing and others in the literature.^{4,5} The cognitive specificity of the stimulation effect will be evaluated by contrasting distancing performance with performance on a control task that differs by the target cognitive process.

Secondary Objective: Establish the feasibility of modulating emotion regulation performance using TMS on novel cortical targets and cognitive mechanisms.

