Aversive pictures from the International Affective Pictures System¹⁴ are used to elicit negative emotional responses. While viewing a picture, the participant either attempts to minimize any emotional response by taking the perspective of a neutral, objective observer (distancing condition), or allows emotional responses to develop naturally (passive control condition). After the regulation period, the participant rates his or her affective state using a valence scale, and for distancing trials, perceived effort expended during regulation. Distancing performance is assessed for each participant by subtracting the average valence rating on natural response trials from distancing trials, yielding the shift toward less negative/more positive valence resulting from regulation. In addition to these two trial types, trials are included in which the participant is cued to respond naturally to positive pictures. These trials are not analyzed, but they reduce predictability in the task and the likelihood of negative mood induction. Finally, trials are included in which participants are cued to regulate negative responses using a distraction technique that is not expected to rely on self-projection or the targeted brain area.^{15,16} For this technique, participants are instructed to silently rehearse a previously learned nine-digit number while viewing the picture. This condition allows for the assessment of whether stimulation-induced effects on distancing performance are related to a process specific to distancing (i.e. self-projection) or processes related to cognitive emotion regulation more generally (e.g. cognitive control, affective self-reflection).

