stimulation and an electrical sham stimulation designed to resemble the scalp sensations of TMS. As indicated in Figure 2, participants will complete one run of the task after each stimulation condition in a counterbalanced design, allowing enough time for stimulation effects to subside between conditions. Participants will also complete a simplified version of the task (“baseline” in Figure 2) designed to briefly estimate the regulation effect of objective distancing at different times throughout the session to confirm that any stimulation-related effects on self-projection have subsided. Finally, participants will be debriefed to assess awareness of stimulation conditions and proper use of techniques during the experimental task.

[figure not shown]

Figure 2.

One hundred healthy young adults (18-39 y.o.) will participate in all parts of the experiment. Participants will have no history of psychiatric or neurological illness and no ongoing psychoactive drug use (for more details see Section 5 below). Normal right-handed volunteers will be recruited from a registry maintained by the Duke Brain Imaging and Analysis Center under Pro00010672, *Screening for Participation in MRI Subject Pool*.

Screening: Participants will complete screening via a REDCap survey to determine eligibility for the study. This survey will include demographic and medical questions to evaluate the inclusion and exclusion criteria for the study including safety contraindications for MRI or TMS. Additionally, participants will complete the BIAC MRI safety screening form and urine pregnancy test (female participants) at the first study appointment before MRI procedures and the TMS adult safety screening form, urine pregnancy test (female participants), and urine drug test at the second study appointment before TMS procedures.

Motor Threshold Determination: All TMS procedures will occur in room 54211 in the Department of Psychiatry and Behavioral Sciences, Duke Clinic South. Motor threshold (MT) is defined as the minimum magnetic flux needed to elicit a threshold EMG response in a target muscle with 50% probability. MT is the standard in the field for determining the intensity of TMS for each individual to reduce seizure risk. The motor evoked potentials (MEP) for the contralateral first dorsal interosseus muscle will be measured with EMG. The scalp region producing the largest amplitude MEP will be identified. At that scalp location, the

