As noted in Rossi et al.,²⁰ Loo and colleagues reported mild and transient changes in auditory threshold in two depressed patients following a 2-4 week course of TMS.²⁴ Cases of tinnitus have been reported after TMS treatments. In addition, in a study investigating the effects of TMS on symptoms of depression, a patient experienced moderate to severe tinnitus after an TMS session in which earplugs were not used. Rossi et al. recommended that hearing protection always should be worn during TMS application, and that individuals with cochlear implants not receive TMS. In the current study, earplugs will be worn by all subjects during TMS procedures. Individuals with cochlear implants will be excluded from participation.

Risks to the unborn children of pregnant women receiving MRI and TMS are unknown. Pregnant women will be excluded as per IRB policy. Female subjects are tested with a urine pregnancy test prior to their first MRI session as per IRB-approved BIAC policy. The person(s) who will perform the urine pregnancy test will have successfully completed training as directed by the Chair of Obstetric and Gynecology of the Duke University School of Medicine. The urine pregnancy test kits used for this research study will be those commercially available test kit specified by the Chair of Obstetric and Gynecology and in routine use at DUHS.

10. Costs to the Subject: There is no cost for subjects to participate in this study.

11. Data Analysis & Statistical Considerations: The primary outcome measure of this study is change in self-reported valence. Specifically, we will compute the difference in mean valence scores between distancing trials and natural response trials. This difference represents the change in valence due to distancing, or its emotion regulatory effect, and this metric has been sensitive to distancing manipulations in our previous experiments. We hypothesize that this difference will be reduced following active TMS relative to sham TMS. We will compute similar analyses for distraction trials relative to natural response trials, hypothesizing no effect of stimulation condition in this case. We will apply repeated-measures analyses of variance with appropriate follow-up tests to conduct these analyses.

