A secondary outcome measure of this study is change in self-reported effort. This measure is not assessed on natural response trials as this condition is intended to be a passive mode of observing the stimuli. Nevertheless, repeated-measures analyses of variance will again be used to evaluate the effects of stimulation on effort scores for distancing and distraction.

12. Data & Safety Monitoring: The subjects will be fully informed of the nature of the study requirements prior to enrollment and periodically throughout the study. The subject's wellbeing will be continuously monitored by the experimenter, and the Principal Investigator will report all serious adverse events in an expedited manner to the DUHS IRB office and all applicable regulatory authorities in accordance with standard operating procedures.

The study monitor will be [name]. [name] will ensure the quality of the study and establish that each co-investigator is complying with the investigational plan and IRB regulations. Monitoring of this protocol is simplified by the fact that this study involves a small number of investigators.

Throughout the investigation, the monitor will ensure that the facilities being used continue to be acceptable for the purposes of the study; that the investigational plan is being followed; that any changes to the protocol have received IRB approval; that accurate, complete, and current records are maintained; and that accurate, complete, and timely reports are made to the IRB. This will be accomplished through quarterly meetings during which the status of the protocol, investigators, and IRB compliance are reviewed. The monitor will review each research chart for completeness and accuracy. He will confirm that inclusion and exclusion criteria have been met for each subject enrolled, and compliance with all other aspects of the investigational plan are met.

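### Section 11 does not name the distancing-versus-distraction test on valence that Section 2 announces, so specificity could be read from one significant and one non-significant result

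*Combined protocol and SAP*

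**What the plan says.** Section 2, under the Primary Objective's measurement, announces the comparison: "The cognitive specificity of the stimulation effect will be evaluated by contrasting distancing performance with performance on a control task". Section 4 identifies distraction as the control and gives its purpose: "This condition allows for the assessment of whether stimulation-induced effects on distancing performance are related to a process specific to distancing", as opposed to "processes related to cognitive emotion regulation more generally".

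Section 11 sets out the valence analysis. The primary measure is mean valence on distancing trials minus natural-response trials, and this difference is expected to shrink under active stimulation relative to sham. Then comes: "We will compute similar analyses for distraction trials relative to natural response trials, hypothesizing no effect of stimulation condition in this case". The method is given in one sentence: "We will apply repeated-measures analyses of variance with appropriate follow-up tests to conduct these analyses". No ANOVA factors, levels or interaction are named.

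For effort, the secondary outcome, the plan says that "repeated-measures analyses of variance will again be used to evaluate the effects of stimulation on effort scores for distancing and distraction". Natural-response trials carry no effort rating, so this reads naturally as a strategy-by-stimulation model, although the interaction is not named there either. The valence text does not take that form.

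**The concern.** Specificity is part of how the Primary Objective is measured, and it is why the distraction condition exists. As written, the valence plan consists of two parallel active-versus-sham analyses, each against natural response, with a reduction predicted for one and no effect for the other. Carried out literally, these never test whether stimulation affected distancing more than distraction.

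A significant effect beside a non-significant one does not show that the two differ. If stimulation impaired both strategies equally, chance alone could make one cross the 5% line and leave the other short of it. The result would look specific to self-projection when it reflected a general effect on emotion regulation, which is the explanation that the distraction condition is meant to exclude.

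**Working it through.** There is no figure in the plan to reproduce, because it gives no alpha, power, effect size, SD or correlation.

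**Inputs.**
- N = 100 (Section 4: "One hundred healthy young adults (18-39 y.o.) will participate in all parts of the experiment").
- Assumed: two-sided 5% tests, no dropout in the main case, normal data and equal SDs of the two contrasts.
- *dz* is the true stimulation effect in SDs of the active-minus-sham difference score, with positive meaning the hypothesised direction. A single paired test at N = 100 has 80% power at dz = 0.283 and 51% at dz = 0.20.
- *ρ* is the correlation between the two contrasts.

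**Choice of ρ.** The plan states: "Distancing performance is assessed for each participant by subtracting the average valence rating on natural response trials from distancing trials". Distraction is analysed against the same natural-response mean. Let A, B and N be the active-minus-sham differences for distancing, distraction and natural response, with common variance v and common covariance c. Then

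Cov(A − N, B − N) = c − c − c + v = v − c, and Var(A − N) = Var(B − N) = 2(v − c), so ρ = (v − c) / [2(v − c)] = 0.5.

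If A and B correlate more with each other than with N, ρ exceeds 0.5. I use 0.5 and 0.7 as lead cases; 0.7 is an assumption and is not derived.

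**Illustration.** Take t = 2.3 for distancing (p = 0.024) and t = 1.5 for distraction (p = 0.14), with equal SDs. The direct test has t = (2.3 − 1.5)/√(2 − 2ρ), which gives p = 0.57 at ρ = 0 and p = 0.43 at ρ = 0.5. There is no evidence of a difference.

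**False specificity when both true effects are equal** (simulation, N = 100). The pattern is distancing significant in the hypothesised direction and distraction not significant. The two-part rule requires both the distancing effect and the direct contrast to be significant in the hypothesised direction.

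| dz | Pattern, ρ 0.5 / 0.7 | Two-part rule, ρ 0.5 / 0.7 |
|---|---|---|
| 0.20 | 16.8% / 12.7% | 2.3% / 2.1% |
| 0.283 | 11.3% / 8.7% | 2.5% / 2.4% |
| 0.40 | 1.9% / 1.5% | 2.5% / 2.5% |

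The direct contrast alone errs in this direction in 2.5% throughout. Hand check at ρ = 0 and dz = 0.20: the pattern probability is 0.508 × (1 − 0.508) = 0.25, as simulated. At ρ = 0.9 it is 7%. With an assumed 80 completers, the pattern occurs in 16% / 13% at dz 0.20 and 14% / 11% at dz 0.283 (ρ 0.5 / 0.7).

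**Why the interaction alone is not enough.** Suppose stimulation leaves distancing unchanged and shifts distraction the opposite way by dz 0.283. The interaction is then significant in the hypothesised direction in 51%, 80% and 95% of trials at ρ = 0, 0.5 and 0.7. The two-part rule gives 2.5%.

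**Power for a truly specific effect** (distraction effect zero, N = 100). The interaction has standardised effect dz/√(2 − 2ρ); for dz = 0.283 this is 0.200, 0.239, 0.283 and 0.365 at ρ = 0, 0.3, 0.5 and 0.7.

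| | ρ 0 | ρ 0.3 | ρ 0.5 | ρ 0.7 |
|---|---|---|---|---|
| dz 0.283, interaction alone | 51% | 66% | 80% | 95% |
| dz 0.283, two-part rule | 49% | 59% | 69% | 77% |
| dz 0.283, side by side | 76% | 76% | 77% | 77% |
| dz giving 80% under two-part rule | 0.40 | 0.35 | 0.32 | 0.29 |

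At dz = 0.20 the two-part rule has power 25%, 34% and 42% at ρ = 0, 0.5 and 0.7, against 48% side by side.

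**The case against.** The strongest reply is that protocol and SAP are one document and Section 2 already commits to the contrast. A repeated-measures ANOVA with condition and stimulation as factors, followed by the two named comparisons, fits Section 11 and contains the interaction. The prediction of no effect on distraction is a hypothesis, and nowhere does the plan say that specificity will be declared from one significant and one non-significant test. On this reading the gap is one of drafting.

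Most of that is fair, and it limits the point: the contrast is not named for valence, and nothing here shows that the investigators intend the wrong inference. But the text fits either analysis, the two can disagree about specificity, and the ANOVAs are tied to the two parallel analyses just described. An analysis plan should settle that choice beforehand.

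Two further objections stand in part. Every error rate rests on assumed quantities, and at dz 0.40 the side-by-side pattern errs slightly less often than the proposed rule. The rule also costs most power where the error it prevents is largest: at dz 0.20 it would miss more than half of truly specific effects. That is a price of the correct test; the higher figure for side-by-side reading comes with a 13% to 17% false-claim rate at the same effect size. Finally, naming the contrast closes the gap by itself. The two-part rule goes further, and its justification is the opposite-shift case shown above, which the plan does not raise.

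**Conclusion.** The concern holds. Section 11 does not turn the specificity comparison announced in Section 2 into a named test on valence, and its two parallel analyses leave room for an invalid inference. With N = 100, two-sided 5% tests, equal true effects and a correlation of 0.5 to 0.7, reading the results side by side would suggest specificity falsely in about 13% to 17% of trials at dz 0.20 and 9% to 11% at dz 0.283. The risk is negligible at dz 0.40. These sizes depend on the assumptions; the omission does not. The primary test of distancing minus natural response, active versus sham, is untouched. This is an inexpensive improvement to the plan and does not undermine the design.

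**What to change.** In Section 11, name as the specificity test on valence, at two-sided 5%:

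(Distancing active − Distancing sham) − (Distraction active − Distraction sham).

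This is the strategy-by-stimulation interaction. The natural-response mean cancels, and the hypothesised sign is negative.

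State that specificity will be claimed only if this contrast and the stimulation effect on distancing minus natural response are both significant in the hypothesised direction. Report the distraction effect with a 95% confidence interval, whose half-width at N = 100 is t(0.975, 99)/√100 = 0.198, or about 0.20 SD, and do not read its non-significance as absence of an effect.

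The cost is two or three sentences, with the same data and design. Specificity becomes harder to claim, so the plan should also state the power of this test at N = 100 over a plausible range of correlations.

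### The primary repeated-measures ANOVA names no run/order or picture term, so any run-by-strategy or picture differences that vary between participants stay in the error of the key contrast

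*Combined protocol and SAP*

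**What the plan says.** Section 4 (Design & Procedures) describes a task in which each trial shows a picture and ends with a valence rating. The negative trials use "Aversive pictures from the International Affective Pictures System". Performance is then reduced to one number per participant: "Distancing performance is assessed for each participant by subtracting the average valence rating on natural response trials from distancing trials". On the two stimulation conditions, Section 4 says that "participants will complete one run of the task after each stimulation condition in a counterbalanced design". The planned sample is 100.

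Section 11 (Data Analysis & Statistical Considerations) repeats the averaging: "we will compute the difference in mean valence scores between distancing trials and natural response trials". The primary hypothesis is "We hypothesize that this difference will be reduced following active TMS relative to sham TMS", and a parallel comparison for distraction predicts no stimulation effect. The method for both is "We will apply repeated-measures analyses of variance with appropriate follow-up tests to conduct these analyses". Section 11 mentions no run, order or picture term and no trial-level model. Effort, the secondary outcome, is also analysed by repeated-measures ANOVA, but it is not rated on natural-response trials.

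The readable text does not give the number of trials per cell, the number of pictures, or how pictures are assigned to strategy and stimulation cells. Section 4 says an earlier task will be adapted, and Figures 1 and 2 are not reproduced in the copy reviewed.

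**The concern.** The primary contrast is a difference of differences over four cells: (distancing − natural) after active stimulation minus the same quantity after sham. Two sources of avoidable noise can enter it.

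- **Run.** Each participant has one active and one sham run, in counterbalanced order. If the distancing effect shifts between runs, through practice, habituation or picture lists tied to run, the shift pushes the contrast one way for those who have active stimulation first and the other way for those who have sham first. Counterbalancing removes the bias, but without an order term the spread stays in the error. A run shift common to both strategies cancels in the difference. Only a run-by-strategy shift matters.
- **Pictures.** If the pictures in each cell differ between participants, differences in how aversive they are add to each participant's contrast as noise. With 100 raters these differences can be estimated well and removed.

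At stake is the precision of the test of the main hypothesis, and of the distraction comparison, where a finding of no effect is informative only if the estimate is tight.

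**Working it through.** The plan gives no alpha, power, effect size or SD, so there is no stated figure to reproduce.

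**Inputs from the document.** N = 100, two runs with counterbalanced stimulation order, participant-mean outcome, ANOVA.

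**Inputs assumed.** Trial residual SD = 1; picture SD *sp* = 0.25–1.0; between-participant SD of the stimulation effect *ss* = 0–1.0; trials per cell *K* = 10–30.

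**Step 1: pictures randomised per participant.** The variance of the estimated contrast is

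- ANOVA on means: [ss² + 4(sp² + 1)/K]/N
- crossed picture intercepts: about [ss² + 4/K]/N

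Mid-case (K = 15, sp = 0.5, ss = 0.5):

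- ANOVA: (0.25 + 4 × 1.25/15)/100 = (0.25 + 0.333)/100 = 0.00583, SE 0.076
- crossed: (0.25 + 4/15)/100 = (0.25 + 0.267)/100 = 0.00517, SE 0.072
- ratio 1.13; saving 0.0667/0.583 = 11.4%

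Over the whole assumed range the ratio runs from 1.007 (K = 30, sp = 0.25, ss = 1.0; saving 0.7%) to 2.00 (sp = 1.0, ss = 0; saving 50%).

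**Step 2: a run-by-strategy shift.** Let δ be the change in (distancing − natural) from run 1 to run 2. The contrast is θ − δ for active-first participants and θ + δ for sham-first participants. With half in each order, the per-participant variance rises from V to V + δ². In the mid-case V = 0.517, so δ = 0.26 raises it to about 0.583, the same loss as in Step 1. Picture lists tied to run give an expected δ² of 4sp²/K = 4 × 0.25/15 = 0.067. An order factor in the ANOVA removes it for one degree of freedom.

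**Step 3: check by assignment scheme.** Mid-case, from 2,000 simulated data sets for the ANOVA and mixed-model equations with known variances for the crossed model:

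| Pictures | ANOVA SE | ANOVA + order SE | Crossed SE | ANOVA type I error |
|---|---|---|---|---|
| Randomised per participant | 0.0763 | 0.0763 | 0.0721 | 5.3% |
| Sets rotated over cells | 0.0765 | 0.0765 | 0.0719 | 4.5% |
| Sets tied to run | 0.0763 | 0.0718 | 0.0719 | 3.3% |
| Same set per cell for everyone | 0.0719 | 0.0719 | 0.268 | 61% (pictures as random) |

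If the same pictures appear in every cell, their main effects cancel and there is nothing to recover.

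In the last row of the table, picture variance is not in the error term. It is common to all participants and so is not divided by N: SE = √(0.0667 + 0.00517) = 0.268. The picture difference is confounded with the contrast.

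**Step 4: power, for illustration.** At N = 100 and two-sided 5%, the ANOVA has 80% power at a standardised paired effect of 0.283. A variance ratio of 1.13 turns this into 0.283 × √1.13 = 0.301, or about 85% power. That is equivalent to about 13 more participants.

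**The case against.** A within-participant ANOVA on means is conventional, and Section 11 says the metric was sensitive in the sponsor's earlier experiments. Nothing in the checks makes it invalid where pictures are randomised, rotated or tied to run: its type I error stayed near or below 5% in the mid-case. That stands. In those cases this is a matter of efficiency.

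The sharper objection is that the loss depends on a picture-assignment rule the text does not give. That also stands. A reader might infer that the ANOVA certainly loses precision. The documents do not support this: the loss is nil if pictures repeat in every cell, and no picture variance reaches the error if sets are fixed per cell. A reader might equally infer from the 61% figure that the trial has a false-positive problem. That figure applies only if every participant sees the same set in the same stimulation-by-strategy cell, which the documents do not say. Nor should the missing assignment rule be called an omission, since the figures not reproduced may show it.

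The size of the gain is also open to challenge. With picture SD 0.5–1.0 and effect SD 0.2–0.6 the saving is 6–48%, and 80% power becomes 83–97%. With picture SD 0.25 and effect SD 1.0 it is only 1–2%. Where lists are tied to run, an order factor in the ANOVA does as well as the crossed model (0.0718 against 0.0719), so the gain should not be credited to picture effects.

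Finally, picture-by-stimulation slopes could cost precision. With 30 pictures per strategy and an assumed slope SD of 0.2, they add 2 × 0.04/30 = 0.0027, giving SE √(0.0052 + 0.0027) = 0.089 against 0.076 for the ANOVA. The change proposed here is therefore limited to picture intercepts.

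**Conclusion.** The point holds in conditional form. Section 11 names no run/order or picture term although the design has two counterbalanced runs and trial-level ratings. Where the distancing effect differs between runs, or picture-to-cell assignment varies between participants, the planned analysis gives away precision that the collected data could recover.

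Under the assumed variances and trial counts the saving is about 1% to 50% of the contrast variance, 11–12% in the mid-case, and zero if the same pictures appear in every cell. None of these values can be confirmed from the documents.

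If sets are fixed per stimulation-by-strategy cell for everyone, the problem is confounding. The model then gains no precision, and the conclusion has to be limited accordingly.

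**What to change.** In Section 11:

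1. Include run (equivalently, stimulation order) and run-by-strategy in the primary analysis of valence, and test the single stimulation × (distancing − natural) contrast.
2. Where pictures vary over cells between participants, fit this as a trial-level linear mixed model on negative-picture trials, with participant random effects and crossed picture intercepts.
3. Prespecify the fallback if the model does not converge: ANOVA on participant means with order as a factor. Keep the participant-mean ANOVA as a sensitivity analysis.
4. State in Section 11, or refer to where it is stated, how pictures are assigned to cells and how many trials each cell has. If a set is the same for everyone within a stimulation-by-strategy cell, say that the contrast is confounded with the picture sets and limit the conclusion accordingly.
5. Use the same model for distraction against natural response. For effort, use only the distancing and distraction levels. The valence model cannot be carried over unchanged, because effort is not rated on natural-response trials.

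The cost is SAP wording and modest programming on ratings already recorded. The downside is a slightly more complex model and one or two degrees of freedom.
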